6 STUDY PERIODS, TREATMENT REGIMENS AND POPULATIONS FOR ANALYSES

6.1 Study Periods

The following periods are defined for this statistical analysis plan:

- The pre-treatment period covers the time period prior to or on the first dose time of single-blind study medication.
- The single-blind treatment period starts at the time of the first dose of single-blind study medication and lasts until :
 - the time of the last dose of single-blind study medication for concomitant medication summaries
 - 56 days post last dose of single-blind study medication for subjects who do not enter OL. For those subjects who do enter OL, the single-blind treatment period lasts until first day of open-label for abatacept randomized subjects or until 10 days post last dose of single-blind treatment for adalimumab randomized subjects for safety analyses (AE and labs).
 - 21 days post last dose of single-blind study medication for subjects who do not enter OL For those subject who do enter OL, the single-blind treatment period lasts until first day of open-label for abatacept randomized subjects or until 10 days post last dose of single-blind treatment for adalimumab randomized subjects for immunogenicity analyses

Note: To align the cut-off of the single-blind treatment period for abatacept and adalimumab and taking into account that for adalimumab there is a wash-out period of 6 weeks, 10 days is

used to cut the single-blind treatment period for adalimumab. Ten (10) is equal to the expected maximum number of days after last single-blind abatacept dose and prior to first open-label abatacept dose (7 days +/- 3 days).

- The open-label abatacept treatment period starts at the time of the first dose of open-label abatacept treatment and lasts until 56 days post last open-label abatacept dose (AE and labs), except for immunogenicity analyses for which the open-label period goes up to 21 days post last open-label abatacept dose.
- The cumulative abatacept period starts at the time of the first dose of abatacept (single-blind or open-label) and lasts until 56 days post last abatacept dose (single-blind or open-label), except for immunogenicity analyses for which the cumulative abatacept period goes up to 21 days post last abatacept dose.

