Extent of exposure to single-blind study drug (abatacept and adalimumab) in the as-treated analysis population will be summarized in two ways; first, by the number of study drug doses, summarizing frequency distribution of number of study drug doses by treatment group, and second, by the number of days the subject is known to be on study drug, ignoring any dosing interruptions.

For subjects who are not treated in the open-label period, exposure to single-blind study drug in days is calculated as:

- exposure = (date of last single-blind study medication - date of first single-blind study medication +1) + 56.

The offset of 56 days represents approximately four times the half-life of abatacept in humans.

For subjects who receive single-blind abatacept study drug and enter the open-label period within 56 days of the last dose of single-blind study medication, exposure to single-blind study drug in days is calculated as:

- exposure = (date of first open-label study medication - date of first single-blind study medication).

For subjects who receive single-blind adalimumab study drug, exposure to single-blind study drug in days is calculated as:

- exposure = (date of last single-blind study medication +10 - date of first single-blind study medication).

To align the exposure of adalimumab with the exposure of abatacept and taking into account that for adalimumab there is a wash-out period of 6 weeks, 10 days is used to adjust the exposure for adalimumab. Ten (10) is equal to the expected maximum number of days after last single-blind abatacept dose and prior to the first open-label abatacept dose (7 days +/- 3 days).

Extent of exposure to abatacept (single blind and open-label) during the cumulative abatacept period will be summarized in two ways; first, by the number of abatacept injections, and second, by the number of days the subject is known to be on abatacept, ignoring any dosing interruptions.

$$\text{exposure} = (\text{date of last abatacept dose} - \text{date of first abatacept dose} +1) + 56.$$

The offset of 56 days represents approximately four times the half-life of abatacept in humans.

Abatacept includes single-blind abatacept and open-label abatacept. Exposure will be summarized for cumulative abatacept population and presented for all subjects in this population combined

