7.7.6 *Multiple Adverse Events*

Several descriptive summaries of adverse events that takes into account the number of occurrences that an AE was reported by individual patients will be provided. In order to prepare these summaries, the CRF data will be processed according to standard BMS algorithms to categorize each line of patient data as a new occurrence or a continuation of an existing event. This

determination will be based upon onset and resolution dates. Each line of patient data will represent the maximum severity observed as well as the last known assessed relationship to study medication by the investigator.

This data will be presented as the rate per 100 years of patient exposure. Exposure to study medication will be calculated according to approved standard BMS algorithms as well.

As an example, if 5 patients report 7 unique episodes of headache and had a combined cumulative exposure of 20 years to study medication, the incidence rate is reported as $7 / 20 * (100)$ or 35 cases per 100 patient years of exposure.

The following summary tables will be provided:

- A table showing the total number and rate (exposure adjusted) of occurrences for all AEs occurring in at least 10% of the subjects treated will be presented for the single-blind period.
- Listing displaying the unique instances of all AEs, i.e., after duplicates have been eliminated and overlapping and contiguous occurrences of the same event have been collapses.

Similar summaries and listings will be done for the cumulative abatacept period.

7.7.7 *Summaries of Laboratory Data*

Safety summaries based on laboratory test results include evaluation of laboratory abnormalities and change in laboratory test values from baseline. The baseline value on a per analyte basis is the last non-missing value prior to the start of single-blind study drug

Laboratory abnormalities are identified using a pre-defined set of marked abnormality criteria. The criteria will be listed in the CSR. The frequencies of laboratory abnormalities will be presented by laboratory test and treatment group during the single-blind treatment period and by laboratory test and all abatacept subject combined into one group for the cumulative abatacept period. The single-blind treatment period and the cumulative abatacept period for the laboratory analyses are defined in [Section 6.1](#).

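### SAP 7.4.1: the adalimumab exposure formula has no open-label condition, so adalimumab subjects not treated in open label have two exposure values 47 days apart

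*SAP*

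**What the plan says.** SAP 7.4.1 (Study Therapy) has three formulas for single-blind exposure in days.

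- **General formula.** Its condition is "For subjects who are not treated in the open-label period, exposure to single-blind study drug in days is calculated as", with no restriction by drug. The formula is "exposure = (date of last single-blind study medication - date of first single-blind study medication +1) + 56".
- **Abatacept formula.** It covers only abatacept subjects who "enter the open-label period within 56 days of the last dose of single-blind study medication", and runs from the first single-blind dose to the first open-label dose.
- **Adalimumab formula.** Its condition is "For subjects who receive single-blind adalimumab study drug, exposure to single-blind study drug in days is calculated as", and nothing more. The formula is "exposure = (date of last single-blind study medication +10 - date of first single-blind study medication"). The reason given is the six-week washout: 10 days is the longest expected gap after the last single-blind abatacept dose and "prior to the first open-label abatacept dose (7 days +/- 3 days").

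SAP 6.1 defines the single-blind period for adverse events and laboratory data. It lasts until "56 days post last dose of single-blind study medication for subjects who do not enter OL", in either arm. The 10-day limit there applies only to adalimumab subjects who do enter open label. SAP 8.5 also writes out the open-label condition when it sets the upper limit of the Week 24 window for adalimumab subjects.

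SAP 7.7.6 plans exposure-adjusted adverse-event rates: "This data will be presented as the rate per 100 years of patient exposure". It takes the exposure from approved standard sponsor algorithms and does not refer to 7.4.1.

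**The concern.** Open label is optional under SAP 2.1, and subjects can also stop early, so adalimumab subjects who never start open-label abatacept are to be expected. Such a subject satisfies the condition of the general formula and that of the adalimumab formula, and the SAP does not say which takes precedence.

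A programmer who follows the arm-specific line would end these subjects' exposure 10 days after the last dose. An abatacept subject with the same dosing dates and no open-label treatment would be credited 56 days. The exposure table is presented by treatment group, so the arms would differ for a reason unrelated to dosing. The error would run in one direction and in one arm only. If the same exposure also served as the denominator in 7.7.6, adverse events would be counted to 56 days over person-time cut at 10 days.

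**Working it through.** **Inputs.** F = day of first dose and L = day of last dose. The offsets are 56 and 10 days (SAP 7.4.1), and the safety period for non-entrants is 56 days (SAP 6.1). For the last planned adalimumab dose, Protocol 4.5.2 prints Day 152, but 14-day steps from Day 1 give 1 + 11 x 14 = Day 155. Those two need reconciling in the protocol; both are shown here and the conclusion does not depend on which is used.

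**The plan's own figure.** The 10-day offset reproduces: 7 + 3 = 10.

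**The two formulas.**

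- General: (L - F + 1) + 56 = L - F + 57
- Adalimumab: L + 10 - F = L - F + 10
- Difference: 57 - 10 = 47 days for any F and L. Of these, 46 come from the offsets (56 - 10) and 1 from the +1 that the adalimumab formula lacks.

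**Check against SAP 6.1.** For a non-entrant, the days from F to L + 56 inclusive number L - F + 57. This equals the general formula exactly. The adalimumab formula falls 47 days short.

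**Single subjects, F = Day 1.**

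| Last dose | General | Adalimumab | Ratio |
|---|---|---|---|
| Day 1 | 57 | 10 | 5.70 |
| Day 29 | 85 | 38 | 2.24 |
| Day 57 | 113 | 66 | 1.71 |
| Day 152 | 208 | 161 | 1.29 |
| Day 155 | 211 | 164 | 1.29 |

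**Arm level.** The mean exposure of the adalimumab arm falls by 47 days times the share not entering open label: 4.7 days at 10%, 9.4 at 20%, 18.8 at 40%.

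For total exposure, assume 40 adalimumab subjects (the increased size in SAP 5). Assume that every switcher has a last dose on Day 155 (164 days), half of the non-entrants complete to Day 155, and half stop at Day 57. The documents give no non-entry rate, so it is varied:

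- 10% (4 subjects): 36 x 164 + 2 x 211 + 2 x 113 = 6552 days, against 36 x 164 + 2 x 164 + 2 x 66 = 6364. Ratio 1.03.
- 20% (8 subjects): 32 x 164 + 4 x 211 + 4 x 113 = 6544, against 32 x 164 + 4 x 164 + 4 x 66 = 6168. Ratio 1.06.
- 40% (16 subjects): 24 x 164 + 8 x 211 + 8 x 113 = 6528, against 24 x 164 + 8 x 164 + 8 x 66 = 5776. Ratio 1.13.

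If this exposure were the denominator in 7.7.6, the adverse-event count would be the same under either formula, so the pooled rate would rise by these ratios.

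**The case against.** The strongest reply is that this is a missing clause whose intent is plain. The washout rationale under the adalimumab formula has meaning only for subjects who switch, SAP 6.1 makes the split explicitly, SAP 8.5 writes the condition out, and the general formula reproduces the 6.1 period to the day. That stands as a reading of intent and limits the severity. It does not remove the ambiguity: the SAP is the specification for programming, and both conditions are met as written.

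A reader might infer that adalimumab exposure will be understated. The documents do not show that. It happens only if the adalimumab formula is applied to non-entrants, and nothing says which formula was programmed.

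A reader might also infer that adalimumab adverse-event rates are inflated, or take 1.29 or 2.24 as the size of the inflation. Neither is supported. SAP 7.7.6 draws exposure from sponsor algorithms that the SAP does not reproduce, and those ratios belong to single subjects, whereas the planned table pools the arm. To read the arm-level excess as a distortion of the on-treatment event rate would further require events to be as frequent in days 11 to 56 after the last dose as during treatment.

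Finally, little rests on these tables. The study is exploratory with no primary or secondary endpoints, the main adverse-event summaries are proportions of subjects, no testing between groups is planned for adverse events, and the rate table covers only events in at least 10% of subjects. All of this stands.

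**Conclusion.** SAP 7.4.1 as written gives adalimumab subjects not treated in open label two exposure values, always 47 days apart, and only the general formula agrees with their safety period in SAP 6.1. This rests on the text and on date arithmetic alone.

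What is established is an ambiguity in a descriptive exposure summary. An effect on the adverse-event rates is conditional on 7.7.6 using this exposure. Its size, about 3% to 13% over 10% to 40% non-entry, rests on the assumed non-entry rates, the assumed mix of completers and Day 57 stoppers, and 40 subjects in the arm. The point is minor, but should be settled because the shift would affect one arm of a head-to-head comparison.

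**What to change.** 1. In SAP 7.4.1, limit the 10-day formula to adalimumab subjects who enter the open-label period.
2. State there that adalimumab subjects not treated in open label use the general formula (+1 + 56).
3. Confirm which formula was programmed for these subjects. SAP 7.7.1 indicates that the single-blind analysis had already been run, so this check comes before any claim that tables are unaffected.
4. State in SAP 7.7.6 whether its denominator is the 7.4.1 exposure. If it is, end each subject's denominator at the adverse-event cut-off actually used. That first requires reconciling the 10 days in SAP 6.1, 7.4.1 and 8.5 with the 20 days that 7.7.1 says were used post hoc for adalimumab subjects who switch. Tying the denominator to 6.1 as it stands would leave 10 days of counted events without matching exposure in those subjects.

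The cost is a clause and a sentence in the SAP, one condition in the exposure derivation, and a check of the existing program. The exposure table, and the rate table if it uses the same variable, would need rerunning only if the adalimumab formula was applied to non-entrants or the cut-off for switchers changes.

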7.4.2 Discontinuation of Study Therapy

[figure not shown]
See [Section 7.3.1](#).

7.4.3 ***Treatment Compliance***

The number of subjects who missed study doses during the single-blind (excluding missed study doses due to premature discontinuation from the study) will be summarized by treatment and number of study doses missed. A corresponding listing of subjects with missed doses during the single-blind period will be provided.

[figure not shown]
In addition, the number of subjects who missed study doses during the cumulative abatacept period (excluding missed study doses due to premature discontinuation from the study) will be summarized for the cumulative abatacept population. A corresponding listing of subjects with missed doses during cumulative abatacept period will be provided.

7.7 Safety

Analysis of all safety data will follow the BMS standard safety data conventions^{2,3} and supplements to the standard conventions for the abatacept programs⁴.

The evaluation of drug safety is based primarily on clinical AEs, vital signs and laboratory abnormalities reported during the single-blind treatment period. All safety presentations for the Week 24 analyses will be based on the as-treated analysis population by treatment group.

All safety presentations for the cumulative abatacept period will be based on the cumulative abatacept population and the presentation will be for all abatacept treated subjects (single-blind and/or open-label) combined into one group.

Frequency distribution and individual listings of all AEs will be generated. Changes in clinical laboratory test results from baseline will be summarized. Laboratory marked abnormalities using pre-defined abnormality criteria will also be descriptively summarized. There will be no statistical testing of group difference with respect to frequencies of AEs or laboratory marked abnormalities.

7.7.1 Adverse Events

All AEs are coded and grouped into Preferred Terms (PT) by System Organ Class (SOC), using the latest approved version of the Medical Dictionary for Regulatory Activities (MedDRA) at the time of database lock. Listings and summaries will be based on the resulting SOCs and PTs.

All reported AEs during the single-blind treatment period and all reported AEs reported during the cumulative abatacept period will be listed, indicating the subjects id, age, gender, the date of onset, the day of onset relative to the start of treatment, investigator's assessment of severity and relationship to study drug.

In addition, all reported AEs during the washout-out period (beyond 20 days past last single blind dose of adalimumab up to first dose of open-label abatacept) will be in a separate listing. This listing will only include adalimumab patients who are treated with OL abatacept. The threshold of 20 days is chosen for this listing, because AEs up to 20 days past last single-blind dose of adalimumab are included in the AE summaries of the single-blind period. It should be noted that for the single-blind analysis a threshold of 20 days (post-hoc) was used instead of 10 days defined in version 1.0 of SAP.

AEs will be summarized for the single-blind treatment period and the cumulative abatacept period. This period is defined in [Section 6.1](#). These AE summaries will be based on proportions, which represent the number of subjects experiencing the AEs divided by the number of subjects who received at least 1 dose of single-blind study medication for the Week 24 analysis and by the number of subjects treated with abatacept for the cumulative abatacept period analysis.

Any AEs irrespectively of when they occur, but will appear on the above mentioned comprehensive listing.

Summary information (the number and percent of subjects by treatment) will be tabulated for the following AEs:

- all AEs including clinical and laboratory AEs
 - most common AEs (reported in 10% of subjects or more in any treatment group)
 - categorized by severity
- related events
 - most common (reported in 5% of subjects or more in any treatment group)
 - categorized by severity
- serious adverse events (SAEs)
- discontinuations due to SAEs/AEs

7.7.2 Adverse Events of Interest

7.7.2.1 Infections

All reported infections and infestations within the SOC: *Infections and infestations* occurring during the single-blind treatment period will be summarized by preferred term and treatment group and also provided in a separate listing. The events will also be summarized by severity.

Similar summaries and listings will be done for the cumulative abatacept period .

7.7.2.2 Malignancy

All events in the MedDRA Maintenance and Support Services Organization (MSSO) malignancies Structured MedDRA Query (SMQ) list occurring during the single-blind treatment period will be captured and reported. These events will be summarized by preferred term and treatment group and will also be listed.

Similar summaries and listings will be done for the cumulative abatacept period .

7.7.2.3 Autoimmune Disorders

The frequency of pre-specified autoimmune disorders, defined using a BMS customized SMQ, occurring during the single-blind treatment period will be provided. Autoimmune disorders occurring during the single-blind treatment period will be summarized by severity. All reported autoimmune disorders occurring during the single-blind treatment period will be listed.

Similar summaries and listings will be done for the cumulative abatacept period.

7.7.2.4 *Injection Adverse Events*

A. Systemic Injection Reactions (pre-specified, defined using a BMS customized SMQ) are defined as systemic AEs (such as hypersensitivity reactions) occurring during the first 24 hours after abatacept/adalimumab SC administration.

B. Local Injection Site Reactions (pre-specified, defined using a BMS customized SMQ) are defined as those AEs that occur at the site of SC injection.

The pre-specified systemic injection reactions and local injection site reactions occurring during the single-blind treatment period will be summarized by severity. These AEs will also be listed.

In addition, a pre-specified local injection site reaction event of interest, defined as the AEs with the following PT that occur at the site of SC injection: *Erythema, Pain, Pruritus, Haematoma, and Swelling* will be summarized by severity.

Similar summaries and listings will be done for the cumulative abatacept period.

7.7.3 *Deaths*

All AEs with the outcome of death reported during the single-blind treatment period will be listed by treatment group, together with a clinical narrative relating to the death of the subjects.

A similar listing will be done for the cumulative abatacept period.

7.7.4 *Other Serious Adverse Events*

SAEs are captured on a CRF page. All SAEs occurring during the single-blind treatment period will be summarized by treatment group and listed.

Similar summaries and listings will be done for the cumulative abatacept period.

7.7.5 *Adverse Events Leading to Discontinuation of Study Therapy*

AEs leading to discontinuation of study drug are identified as those AEs with an action code of 5 on the eCRF page (5 = discontinued study drug). All such AEs occurring during the single-blind treatment period will be listed and summarized by SOC, PT and treatment group. In addition, a listing of subjects with SAEs leading to discontinuation will be provided.

Similar summaries and listings will be done for the cumulative abatacept period.

7.7.6 *Multiple Adverse Events*

Several descriptive summaries of adverse events that takes into account the number of occurrences that an AE was reported by individual patients will be provided. In order to prepare these summaries, the CRF data will be processed according to standard BMS algorithms to categorize each line of patient data as a new occurrence or a continuation of an existing event. This

determination will be based upon onset and resolution dates. Each line of patient data will represent the maximum severity observed as well as the last known assessed relationship to study medication by the investigator.

This data will be presented as the rate per 100 years of patient exposure. Exposure to study medication will be calculated according to approved standard BMS algorithms as well.

As an example, if 5 patients report 7 unique episodes of headache and had a combined cumulative exposure of 20 years to study medication, the incidence rate is reported as $7 / 20 * (100)$ or 35 cases per 100 patient years of exposure.

The following summary tables will be provided:

- A table showing the total number and rate (exposure adjusted) of occurrences for all AEs occurring in at least 10% of the subjects treated will be presented for the single-blind period.
- Listing displaying the unique instances of all AEs, i.e., after duplicates have been eliminated and overlapping and contiguous occurrences of the same event have been collapses.

Similar summaries and listings will be done for the cumulative abatacept period.

7.7.7 *Summaries of Laboratory Data*

Safety summaries based on laboratory test results include evaluation of laboratory abnormalities and change in laboratory test values from baseline. The baseline value on a per analyte basis is the last non-missing value prior to the start of single-blind study drug

Laboratory abnormalities are identified using a pre-defined set of marked abnormality criteria. The criteria will be listed in the CSR. The frequencies of laboratory abnormalities will be presented by laboratory test and treatment group during the single-blind treatment period and by laboratory test and all abatacept subject combined into one group for the cumulative abatacept period. The single-blind treatment period and the cumulative abatacept period for the laboratory analyses are defined in [Section 6.1](#).

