### **3.1.2 Treatment Period (Day 1 to Week 24)**

On Day 1, subjects will be randomized to one of two parallel treatment arms in a 1:1 ratio:

- 1) Abatacept SC (125 mg) weekly
- 2) Adalimumab SC (40 mg) once every two weeks

The Treatment Period duration is 24 weeks.

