#### **4.5.1      *Abatacept Treatment Arm***

On Day 1, subjects will self-administer abatacept 125 mg SC from a pre-filled syringe. On Day 8, subjects will self-administer abatacept 125 mg SC. Thereafter, subjects will self-administer abatacept 125 mg SC once every 7 days, up to and including Week 23 (Day 162).

Treatment duration is 167 days for all randomized subjects (who have not discontinued study therapy).

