#### **4.5.2      *Adalimumab Treatment Arm***

Subjects randomized to adalimumab will self-administer an initial dose of adalimumab 40 mg SC from a pre-filled syringe on Day 1. On Day 15, subjects will self-administer adalimumab 40 mg SC. Thereafter, subjects will self-administer adalimumab 40 mg SC once every 14 days, up to and including Week 22 (Day 152).

Treatment duration is 167 days for all randomized subjects (who have not discontinued study therapy).

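### Systemic injection reactions are counted in 24-hour windows, and abatacept has about twice as many windows as adalimumab: add a per-injection rate

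*SAP*

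**What the plan says.** SAP 7.7.2.4 separates two kinds of injection event. Systemic reactions are "pre-specified, defined using a BMS customized SMQ) are defined as systemic AEs (such as hypersensitivity reactions"), and they qualify by timing: "occurring during the first 24 hours after abatacept/adalimumab SC administration". Local reactions are defined by where they occur, with no time window. For the tables, "The pre-specified systemic injection reactions and local injection site reactions occurring during the single-blind treatment period will be summarized by severity", and the events are listed.

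SAP 7.7.1 bases adverse event summaries on the share of treated subjects with the event. SAP 7.7 presents Week 24 safety data by treatment group and rules out statistical testing of adverse event frequencies between groups.

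The injection schedules differ. Protocol 4.5.1 gives abatacept "once every 7 days, up to and including Week 23 (Day 162"). Protocol 3.1.2 lists "Adalimumab SC (40 mg) once every two weeks", and Protocol 4.5.2 continues it "once every 14 days, up to and including Week 22 (Day 152").

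Two other parts of the SAP bear on the denominator. SAP 7.4.1 summarizes single-blind exposure in one of its two forms "by the number of study drug doses", by arm. SAP 7.7.6 adds exposure-adjusted figures for adverse events seen in at least 10% of subjects: "This data will be presented as the rate per 100 years of patient exposure". Nowhere are reactions divided by injections.

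**The concern.** For systemic reactions, closeness in time to an injection does the attribution; the definition asks for no judgement of cause. Every injection therefore opens a one-day window in which an unrelated listed event can be counted. The text does not say that the window follows each injection, but no other reading fits repeated dosing.

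If one arm has twice as many windows, the by-subject proportions differ even when the drugs behave identically. The tables place the arms side by side in a head-to-head study, so readers will compare them whether or not a test is run. What is at stake is the fair reading of one descriptive safety table. No endpoint or formal conclusion depends on it.

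**Working it through.** **Number of windows.** Injections = 1 + (last dosing week ÷ interval in weeks).

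- Abatacept (Protocol 4.5.1): 1 + 23/1 = 24. Day check: 1 + 7 × 23 = 162, which agrees with the stated day.
- Adalimumab (Protocol 4.5.2): 1 + 22/2 = 12. Day check: 1 + 14 × 11 = 155, but the section says Day 152. Taken literally, Day 152 leaves 11 on-grid injections, the last on Day 141.

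The windows cover 24/168 = 14.3% of a 168-day period under abatacept and 12/168 = 7.1% under adalimumab.

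**Coincidental events.** Let λ be the background rate of listed systemic events per subject-year, equal in both arms and unrelated to injection timing. With k one-day windows and full adherence, P(at least one counted event) = 1 − exp(−λk/365.25). The documents give no λ, so the values below are assumptions.

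| λ | Abatacept, k = 24 | Adalimumab, k = 12 | Ratio | Gap (points) | Expected subjects, 40 per arm |
|---|---|---|---|---|---|
| 0.1 | 0.65% | 0.33% | 2.00 | 0.3 | 0.26 vs 0.13 |
| 0.5 | 3.23% | 1.63% | 1.98 | 1.6 | 1.29 vs 0.65 |
| 1 | 6.36% | 3.23% | 1.97 | 3.1 | 2.54 vs 1.29 |

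With 11 adalimumab injections, the ratio at λ = 1 is 2.14. With 40 per arm (the increased size in SAP 5), the chance that abatacept shows more cases than adalimumab from coincidence alone is 21%, 52% and 65% for the three rates.

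**Adding genuine reactions.** Let r be the share of genuine reactors, equal in both arms, and let a and b be the coincidental probabilities for abatacept and adalimumab. The reported ratio is (r + (1 − r)a) / (r + (1 − r)b).

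| λ | r = 2% | r = 5% | r = 10% |
|---|---|---|---|
| 0.1 | 1.14 | 1.06 | 1.03 |
| 0.5 | 1.44 | 1.23 | 1.13 |
| 1 | 1.59 | 1.37 | 1.22 |

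If genuine reactors are instead 5% under abatacept and 10% under adalimumab (true ratio 0.5), the reported ratio is 0.55, 0.70 and 0.86 for λ = 0.1, 0.5 and 1. At λ = 1: (0.05 + 0.95 × 0.0636) / (0.10 + 0.90 × 0.0323) = 0.110/0.129 = 0.86.

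**Patient-years do not help.** Take completers who continue to open label, with the formulas in SAP 7.4.1. Abatacept exposure is 169 − 1 = 168 days if open label starts on Day 169. Adalimumab exposure is 155 + 10 − 1 = 164 days. The exposure ratio is 168/164 = 1.02, against an injection ratio of 24/12 = 2.

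**Per injection.** Coincidental events occur at λ/365.25 per injection in both arms. At λ = 1 that is 0.27 per 100 injections in each arm, a ratio of 1.00.

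**The case against.** The strongest reply is that risk per subject over a 24-week course is a legitimate measure. The trial randomizes regimens, and more frequent injection is part of the abatacept regimen. A per-injection rate answers a different question and can mislead. Suppose 4 of 40 subjects in each arm react once, at the first dose. With full adherence the rates are 4/960 = 0.42 and 4/480 = 0.83 per 100 injections, which favours abatacept although the risk per subject is the same. This stands. It is a reason to keep the by-subject table and show both figures, and it rules out calling the by-subject figures non-comparable.

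It is also true that the study is exploratory, that no between-arm safety test is planned, that the query list filters out most unrelated events, and that the individual events are listed. These points limit the importance; they do not remove an imbalance of known direction. The query list and the sponsor's safety conventions cited in SAP 7.7 are not in the documents, so a further attribution rule there cannot be excluded.

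Three stronger readings are tempting, and the documents do not support them.

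- A reader might infer that unrelated events alone will make abatacept look twice as reactogenic. That needs nearly every counted event to be coincidental; the second table in the working shows how quickly the ratio falls.
- A reader might infer a gap of about 10 points by assuming one listed event per 100 subject-days: 1 − exp(−0.24) = 21.3% versus 1 − exp(−0.12) = 11.3%. That rate would give 1 − exp(−1.68) = 81% of subjects an unrelated listed systemic event within 168 days, which is implausible for a filtered list.
- A reader might infer that this distorts a protocol event of special interest. Protocol 8.4.3 names injection site reactions, which are the local category and have no time window.

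**Conclusion.** The unequal opportunity is real and follows from the documents: 24 windows against 12, or 11 if Day 152 is read literally, with no per-injection denominator planned. It roughly doubles the coincidental part of the abatacept figure relative to adalimumab, and only that part. The size given here assumes equal, constant background rates of 0.1 to 1 listed events per subject-year, full adherence, and no attribution rule beyond the list and the 24 hours. On those terms the excess is at most about one subject with 40 per arm, and the observed table will often not show it. Local reactions are not affected by this mechanism. Nor is the cumulative abatacept period, which has a single combined group. This is a cheap improvement to a descriptive table, not a threat to the trial's conclusions.

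**What to change.** In SAP 7.7.2.4, for systemic reactions in the single-blind period:

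- Keep the by-subject table, labelled as risk per treatment course.
- Add one descriptive line by arm: systemic reactions per 100 injections given, with the injection counts derived under SAP 7.4.1 as the denominator.
- Footnote that the planned schedules give a 24:12 ratio of 24-hour windows, so coincidental events are more likely to be counted under abatacept.

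No count model is needed with so few expected events, and nothing need change for local reactions or the cumulative period. Separately, the sponsor should reconcile Week 22 with Day 152 in Protocol 4.5.2, since the number of adalimumab windows depends on it.

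The cost is one extra row from data already derived. The downside is a second metric to explain, with a note that the per-injection rate can favour the more frequent regimen if genuine reactions cluster in early doses.
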